**3. \* Describe the study's specific aims or goals. Use lay language whenever possible.**

Our team also investigates the barriers faced by MAW in the US healthcare system by evaluating the cultural competency of healthcare providers related to the Muslim culture at the VCU health system. Our ongoing work with the Muslim community has informed us about the community's needs. In this project, we will implement an interventional program guided by a community-based participatory approach utilizing expert-led education sessions and peer-led interventions, which combine health-related religious teachings and scientific information about the benefits of CC-S and HPV-Vax. The Muslim Community Partners (MCPs) will collaborate with our institute (VCU) by reaching out to four Islamic religious centers in Virginia. Partnership with Islamic centers is valuable to our project due to their ability to convince women to join our study, reach out to a high number of MAW, and because religious voices will be a good motivator for Muslim families to change. The primary outcome is increasing awareness of cervical cancer prevention methods. The secondary outcome is the acceptability and confidence/trust in cervical cancer prevention methods such as CC-S and HPV Vax.

The research questions are: Would MAW intend to do cervical cancer screening and uptake the HPV Vaccination after an education program supported by the Mosques that they frequently visit?

The aims of the study are:

Aim 1b. We will conduct individual interviews with key stakeholders in our Community Advisory Board (Muslim religious leaders (N=4)) to receive feedback on the developed materials and inform the intervention program. This aim includes the Phase II (Preliminary Testing) of the ORBIT model (proof of concept, prepare the pilot).

Aim 2. We will test the preliminary efficacy of the religiously tailored and culturally appropriate intervention program. H1. Participants will show significant improvements in knowledge and acceptance of cervical cancer prevention after the intervention. To test this hypothesis, we will conduct a pre-post survey to examine changes in knowledge and acceptance of cervical cancer screening and prevention. This aim includes the Phase III (Efficacy) of the ORBITT model.

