**2. If this is a multi-Center Project, what is the maximum anticipated number of subjects across all sites?**

**3. Provide justification for the sample size by explaining how you arrived at the expected number of participants and why this number is adequate for answering the research questions:**

Sample: A non-probability sampling (convenience sampling) method will be adopted to allow reach all potential participants. The team members will approach potential respondents at Islamic centers to participate in this study. The inclusion criteria include women aged  $\geq 18$  years who speak English, self-identify as Muslim, and have not participated in our pilot study before. The exclusion criteria are any participants who participated in our pilot study or are unable to provide valid consent (e.g., developmental disability).

Qualitative analysis side: to develop the education material we will recruit 10 female participants above 18 years old who identify as Muslim to participate in the design of the religiously tailored and culturally appropriate education materials for the intervention. First the focus group will help select the targets of the proposed education and the content to achieve each target (design). As a next step the focus group will focus on the formatting of the material, including basic usability testing (refine). Based on information from these sessions we will finalize the educational material for our intervention.

we will use the grounded theory for complete the analysis

Statistical Analysis for quantitative side : We assume that our study's CC-S HPV-Vax uptake rate would increase by 10% post-intervention. Based on a power analysis assuming the use of the student T-test to assess the difference in outcome between the intervention and control groups. The target sample size is estimated based on the G power software sample size calculator for the minimal sample size needed for an unlimited population size using a confidence interval of 80%, a standard deviation of 0.5, and a margin of error of 5%. The study requires 10 participants for intervention to test the feasibility of the program.

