H1. Participants will show significant improvements in knowledge and acceptance of cervical cancer prevention after the intervention. To test this hypothesis, we will conduct a pre-post survey to examine changes in knowledge and acceptance of cervical cancer screening and prevention. This aim includes the Phase III (Efficacy) of the ORBITT model. Aim 3. We will test the feasibility and acceptability of the religiously tailored and culturally appropriate intervention program which includes education and experiential practice/communication skills training. We will recruit 20 participants with the same eligibility criteria as in Aim 1, who have not participated in our previous studies, and conduct a single-arm pilot trial. H2. We hypothesize that the religiously tailored and culturally appropriate intervention program will be feasible to conduct as evidenced by meeting enrollment targets and the ability to implement the program as planned. H3. The intervention will be acceptable as evidenced by engagement (>60%) and retention (>80%), and satisfaction survey ratings.

For these aims, we will use a survey that includes:

Pre-test survey, the scales are:

1. Demographic
2. Perceived Discrimination
3. Religious Discrimination
4. Spiritual Health Locus of Control
5. Modesty
6. Cervical Cancer Knowledge
7. Perceived risk
8. Cuse of action
9. Self-efficacy
10. Attitude about CC screening
11. HPV vaccination acceptability

Post-test survey, the scales are:

2. Perceived Discrimination
3. Religious Discrimination
4. Spiritual Health Locus of Control
5. Modesty
6. Cervical Cancer Knowledge
7. Perceived risk
8. Cuse of action
9. Attitude about CC screening
10. HPV vaccination acceptability
11. General Self-Efficacy Scale (GSES)
12. Cervical Cancer Screening Self-Efficacy Scale

Satisfactory survey are:

- Experience with the intervention.
- Acceptability of content
- Acceptability of delivery

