**See the help text for additional guidance**

**1. A statement explaining the study design**

**Study Design:**

The proposed study consists of two parts.

Part 1 involves formative research through a focus group to gather insights and reach saturation.

Part 2 is a single-arm pre and post-test trial with the objective of evaluating the efficacy of an educational interventional program.

The study aims to increase cervical cancer screening (CC-S) and HPV vaccine (HPV-Vax) rates among Muslim American women (MAW) in Virginia, leading to a reduction in cervical cancer (CC) incidence and mortality.

2. A detailed description of all the procedures that will be followed to carry out the study, preferably in sequential order, and in sufficient detail that the study's methods could be replicated.
  - a. Part 1 - Formative Research: Conduct a focus group with 10 participants until saturation is reached.
  - b. Part 2 - Single-arm Pre and Post-test Trial: Enroll 20 participants to evaluate the educational program's effectiveness.

Participants will complete a baseline survey to assess their knowledge, attitudes, CC-S and HPV-Vax practices, and predisposing factors.

The survey will cover topics such as CC knowledge, experiences of medical mistrust, discrimination, spiritual coping, and fatalism.

3. The schedule and frequency of when and how procedures will be conducted (e.g. in person, online, phone, paper, etc.)

All procedures will be conducted in person at the Islamic Centers, except for follow-up phone calls.

Recruitment will occur during regular Friday prayers and religious holidays.

Participants will receive a brochure explaining the study and be screened for eligibility by the Research Assistant (RA). Eligible participants will be given a telephone contact for enrollment at a more convenient time.

The consent process will involve verbal explanation, providing the consent form in English, and allowing participants to ask questions. Follow-up surveys and confirmations will be conducted via phone calls.

4. A description of all research measures/tests/interventions that will be used, including analyses/tests conducted on specimens/biological samples (if applicable)

**Power Analysis:** No power analysis for this study. A target sample size of 20 participants has been determined based on PhD committee, the purpose of the project is training for the STUDENT.

Measures: Validated scales and surveys will be used to measure

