The primary outcome in increase the number of women who undergo cervical cancer screening. Secondary outcomes include an increase in knowledge and awareness, an increase in self-efficacy, and improvement in attitudes towards cervical cancer prevention.

Long-term outcomes include a reduction in cervical cancer incidence and mortality, sustainability of behavior change, and a reduction in healthcare costs associated with advanced-stage cancer treatment.

Moderator factors that can influence the effectiveness of the program include age, education level, ethnicity, socioeconomic status, Mediating mechanisms that explain how the program leads to its outcomes include improved knowledge and awareness, increased self-efficacy, attitude change, increased and social support,

Identifying and addressing moderator factors and mediating mechanisms can help to tailor the program to the specific needs and preferences of the target population and maximize its effectiveness

**Key Study Variables:** Socio-demographic variables, cultural/religious practices, cancer literacy, knowledge, perceived risk, barriers, benefits, and participation in preventive measures.

**Evaluation Measures:** Intervention acceptance will be self-reported, covering challenges, barriers, facilitators, likes/dislikes, and suggestions for improvement.

This study aims to address barriers to CC prevention among MAW through an educational intervention, using a sequential approach of formative research and a single-arm trial. The study will be conducted at Islamic Centers, involving in-person procedures, phone follow-ups, and self-report measures. The proposed methods are designed to evaluate the effectiveness of the educational program and its impact on CC-S and HPV-Vax rates in the target population.

**Statistical Tests:** Statistical tests such as t-tests or ANOVA can be used to analyze the data from the pre-post survey. These tests will help determine whether there are statistically significant differences between the pre- and post-survey results and whether the intervention had a significant effect on participants' knowledge and acceptance of cervical cancer prevention.

**7. \* The IRB only reviews research activities, so indicate for each of the study activities described in the question above or in the protocol which activities are:**

- Being performed exclusively for research purposes (i.e. they would not otherwise be done apart from this study) **VERSUS**.

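### The plan names two different primary outcomes, awareness and number of women screened, and the screening version has no hypothesis, suitable test or dated follow-up in the text shown

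*Combined protocol and SAP*

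**What the plan says.** **Primary outcome.** Background, Rationale and Goals, question 3, and Study Procedures, question 2, both state: "The primary outcome is increasing awareness of cervical cancer prevention methods". Acceptability and confidence or trust are secondary there. Study Procedures, question 6, item 4 (Outcomes) states: "The primary outcome in increase the number of women who undergo cervical cancer screening". It continues: "Secondary outcomes include an increase in knowledge and awareness".

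**Hypotheses.** H1 reads: "Participants will show significant improvements in knowledge and acceptance of cervical cancer prevention after the intervention". H2 concerns feasibility and H3 acceptability. The research question asks about intention.

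**Tests.** The sample size justification (Study Population, question 3) assumes "the student T-test to assess the difference in outcome between the intervention and control groups". Study Procedures, question 6, says "Statistical tests such as t-tests or ANOVA can be used to analyze the data from the pre-post survey", and gives knowledge and acceptance as the target of those tests.

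**Effect and size.** The sample size justification assumes that a combined screening (CC-S) and vaccination (HPV-Vax) "uptake rate would increase by 10% post-intervention", and asks for 10 intervention participants. Study Procedures, question 6, describes a single-arm pre-post trial of 20 and states "No power analysis for this study". Under direct benefits (Background, question 5), most women are expected to seek screening by the end of the programme.

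**Measurement.** The example screening item asks whether the woman has ever had a Pap smear. Questions on frequency and timing are optional additions. Follow-up surveys are by phone, with no interval given.

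**Survey order.** The summary of the intervention (Study Procedures, question 4) places the month 0 baseline survey after the education and refers to two groups. The survey lists, the baseline survey in question 6 and the Compensation section all require a pre-test. The recruitment text in question 4 has baseline surveys scheduled with participants.

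**The concern.** Awareness is primary in two places and secondary in a third, and all three are current text. If few women are screened, a knowledge gain can be reported as the primary result by citing the aims sections. If several are screened, the Outcomes paragraph can be cited instead. The choice also decides what the trial can answer, because 20 women give useful precision on a change in a score but very little on the 10% rise in uptake that the plan assumes.

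The survey-order sentence is a separate matter. Followed literally, it leaves H1 without a pre-intervention value.

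**Working it through.** **1. Is screening covered by a hypothesis, test and time point?**

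| Element | Awareness or knowledge | Number of women screened |
|---|---|---|
| Formal hypothesis | H1 | none in H1 to H3 |
| Named test | t-tests or ANOVA, pre-post | t-test against a control group that the design lacks |
| Measure | Cervical Cancer Knowledge scale on both survey lists | example item on lifetime Pap smear |
| Time point | pre-test and post-test | phone follow-up without an interval |

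A woman already screened at baseline cannot register new screening on a lifetime item.

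**2. The plan's own figure.** The sample size text gives an 80% interval, SD 0.5 and margin 0.05. The usual formula is n = (z × SD / E)² = (1.2816 × 0.5 / 0.05)² = 164.2, so 165, not 10. The point does not rest on this, but that paragraph cannot support either primary outcome.

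**3. The assumed rise in 20 women.** Assumptions: two-sided alpha 0.05 (the plan states none); the combined 10% read as 10 percentage points of screening alone; no yes-to-no changes, as suits a lifetime item. The rise is 0.10 × 20 = 2 women. The exact 95% CI for 2/20 is 1.2% to 31.7%.

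*Exact McNemar.* With k converters and no reversals, p = 2 × 0.5^k.
- k = 2: p = 0.50
- k = 5: p = 0.0625
- k = 6: p = 0.031

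Six converters are needed. P(Bin(20, 0.10) ≥ 6) = 0.011. With 16 women (80% retention) it is 0.003. If 5% reversed and the net rise stayed at 10 points, it is 0.032 with 20 women.

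*Paired t-test on 0/1 changes*, the family that the plan names. At 4 of 20 the mean is 0.20, the SD is √(20/19 × 0.2 × 0.8) = 0.410 and the SE is 0.410/√20 = 0.0918. So t = 2.18 on 19 df and p = 0.042. At 3 of 20, t = 1.83, which is below the critical value of 2.09. Four are needed, and P(Bin(20, 0.10) ≥ 4) = 0.133.

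**4. Larger effects.** By exact McNemar, 80% power needs true conversion of about 37% with 20 women, or about 78 women at 10%. If most women is read as 50% conversion, P(Bin(20, 0.5) ≥ 6) = 0.979.

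**5. Knowledge score.** A two-sided paired t-test at 0.05 has 80% power for 0.66 SD of the change with 20 women, and 0.75 SD with 16.

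**The case against.** This is a student pilot that says it has no power analysis, so low power for uptake is already conceded. That stands: the point asks for no power and no extra women. But a pilot that claims significant improvement, and an evaluation of impact on screening and vaccination rates, still needs one primary outcome.

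The survey and timeline files are listed but not visible, and the analysis text in the sample size section breaks off. They may contain dated items or a suitable test. That also stands, so those points are limited to the text shown. Unseen files cannot remove the contradiction between the aims sections and the Outcomes paragraph.

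Several stronger readings are tempting, and the documents do not support them:
- *Twenty women could detect no screening effect.* The expectation that most women will seek screening would be detectable. The difficulty there is attribution without a control arm.
- *Six converters are always needed.* That threshold belongs to exact McNemar, which the plan does not name. A paired t-test needs four.
- *There is no pre-test, so H1 cannot be computed.* Several sections require a pre-test and baseline surveys are scheduled. The month 0 sentence is probably a wording error.
- *The three-hour event proves that a survey is missing.* It budgets one 45-minute survey, but a separately scheduled baseline is compatible with that.
- *There is no follow-up.* Phone follow-up is stated but undated, and it may simply be the post-test.

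**Conclusion.** The plan has two incompatible primary outcomes, and this must be fixed before data are analysed. In the text shown, the screening version lacks a hypothesis, a test that fits a paired yes/no outcome in one arm, and a dated assessment. At the plan's assumed rise, the chance of significance with 20 women is about 1% by exact McNemar and 13% by a paired t-test. These figures rest on an assumed two-sided alpha of 0.05, on reading a combined 10% as 10 points of screening, and on no reversals. Screening before baseline would leave fewer women able to convert; no baseline rate is given for these women.

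The knowledge score is the outcome that this design can estimate with useful precision, though its change would also be uncontrolled. The month 0 sentence is a smaller, separate error. Confidence in the outcome conflict is high because it is read directly from the text.

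**What to change.** 1. In both aims sections and the Outcomes paragraph, use one sentence: *The primary outcome is the within-woman change from pre-test to post-test in the Cervical Cancer Knowledge score, tested with a paired t-test at two-sided alpha 0.05.* The investigator must first confirm that this scale is the measure of awareness, because no section says so. Acceptance, measured by the screening-attitude and HPV-vaccination-acceptability scales, becomes secondary. Report the change as uncontrolled. The study ID must match each woman's two surveys.
2. In the summary of the intervention, put the baseline survey before the session and the post-test after it, and delete the reference to two groups. Make the event schedule (Behavioral Intervention/Task Details, question 1) and the intervention-group consent section, which takes consent at the session, agree with when baseline and consent occur.
3. In Outcomes, make screening and vaccination uptake descriptive: n/N with an exact 95% CI among women without prior screening or vaccination, at one stated interval if the phone follow-up is a separate contact.
4. In the sample size justification, delete the 10% uptake assumption, the control-group t-test and the requirement for 10 participants. State 20 as a pilot number without a power analysis, as question 6 does. Delete the claim in question 6 to evaluate impact on screening and vaccination rates.

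**Cost.** No extra participants. Most of this is wording, but the baseline survey and consent need a workable slot before the session. The real downside is giving up the uptake claim.

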The intervention group will consist of 20 participants who will receive one education session divided into three sections/videos. The session will be offered in a single day and last 1.5 hours. The session will include the following topics: 1) Risk of HPV infection (30 minutes), 2) Cervical cancer risk (30 minutes), and 3) Advantages and benefits of early screening and the HPV vaccine (30 minutes).

All participants from both groups will be given the survey at month 0 (baseline) after the delivery of the educational material. The survey will be self-report, available in both hard copy and electronic form with a QR code for Redcap.

Participants are expected to take approximately 45 minutes to complete the survey.

The Islamic center offer private room to practice the research activities in both phases ( Focus group and single arm trial)

**5. \* Does this study have a separate protocol document (i.e. a multisite or sponsor's protocol) that contains a detailed description of the study's methodology?**

Yes

No

**6. \* Since a separate protocol document is not uploaded, describe the proposed research using language understandable to those IRB committee members whose expertise is not scientific. The description must include:**

- 1. A statement explaining the study design**
- 2. A detailed description of all the procedures that will be followed to carry out the study, preferably in sequential order, and in sufficient detail that the study's methods could be replicated**
- 3. The schedule and frequency of when and how procedures will be conducted (e.g. in person, online, phone, paper, etc.)**
- 4. A description of all research measures/tests/interventions that will be used, including analyses/tests conducted on specimens/biological samples (if applicable)**

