**2. \* Describe how data will be linked or unlinked to identifiers including email addresses, names, and/or IP address.**

In this study, data will be collected and stored in a manner that ensures the protection of participants' confidentiality and privacy. Specifically, data will be unlinked from identifiers such as email addresses, names, and IP addresses. For the survey data collected through the REDCap platform, participants' responses will be de-identified. This means that personal identifying information, such as names and email addresses, will not be linked to their survey responses. Instead, each participant will be assigned a unique study ID or code, which will be used to anonymize their data. This separation of identifiers from survey responses helps maintain the confidentiality of participants' information.

Regarding the note recordings using the Apple system, it is important to note that the research assistant will not use any names or identification during the interviews. This further ensures that participants' personal information remains unlinked from the recorded data.

By unlinking data from identifiers, the study aims to protect participants' privacy and confidentiality throughout the data collection and analysis process. It reduces the risk of unauthorized access or disclosure of sensitive information, promoting ethical research practices.

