**Phone Numbers**

- Facsimile Numbers
- E-mail Addresses
- Medical Record Numbers
- Device Identifiers
- Biometric Identifiers
- Web URLs
- IP Addresses
- Account Numbers
- Health Plan Numbers
- Full Face Photos or Comparable Images
- License/Certification Numbers
- Vehicle ID Numbers
- Other Unique Identifier
- No Identifiers
- Employee V#

9. \* If the study will code (i.e. de-identify) the research data by replacing subjects' names and/or other identifiers with assigned subject IDs, explain the following aspects of the coding process:

- The process for how subject IDs will be generated/assigned (e.g. random, sequential)
- Whether there will be a key that links the subject ID with direct identifiers. If there will be no linkage key, state that.

If a key will be created, describe

- The place where the key will be stored
- The role(s) of all individuals who will have access to the key
- When the key will be destroyed

See the help text for guidance.

In this study, the research data will be coded by replacing participants' names and other identifiers with assigned subject IDs to ensure confidentiality and protect privacy. The coding process will follow the following aspects:

**Generation/Assignment of Subject IDs:** Subject IDs will be generated using a random assignment process. Each participant will be assigned a unique identifier that is unrelated to their personal information or characteristics. This random assignment helps maintain anonymity and protects the participants' identities.

**Linkage Key and Storage:** A linkage key will be created to associate the original patient identifiers with the assigned subject IDs. However, in this study, there will be no linkage key that links the subject ID back to direct identifiers. The coding process ensures that the data remains de-identified and confidential.

**Storage of the Linkage Key:** If a linkage key were created, it would be stored separately in the secure REDCap database. Only the Principal Investigator (PI) would have access to the linkage key. The PI would be responsible for safeguarding the confidentiality of the key and ensuring that access is restricted to authorized individuals.

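### The single-arm pre-post survey of 20 women is not tied to a within-woman analysis: no paired test is named, the linkage-key statements conflict, and the timing of the baseline survey is contradictory

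*Combined protocol and SAP*

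**What the plan says.** **Design.** Study Procedures, question 6, states that "Part 2 is a single-arm pre and post-test trial", with 20 women to be enrolled. H1 expects improved knowledge and acceptance, assessed by a pre-post survey. The Compensation page pays separately for a pre and a post survey, so two surveys per woman are intended.

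**Test.** The Statistical Tests paragraph of the same answer says "Statistical tests such as t-tests or ANOVA can be used to analyze the data from the pre-post survey". The only specific test is in the sample-size text (Study Population, question 3), which describes a power analysis "assuming the use of the student T-test to assess the difference in outcome between the intervention and control groups". Question 6 of Study Procedures says instead "No power analysis for this study". The closing summary of the background still calls the design two-armed.

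**Matching.** Active Internet Data Collection, question 2, says "each participant will be assigned a unique study ID or code". Data Confidentiality and Storage, question 9, says "Each participant will be assigned a unique identifier that is unrelated to their personal information or characteristics". That answer first says a key linking identifiers to IDs will be created, and in the next sentence that there will be none. Question 3 of the same page provides for storing a key. The rest of question 9 gives the principal investigator sole access and has keys destroyed after the study.

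**Timing and mode.** Study Procedures, question 4: "All participants from both groups will be given the survey at month 0 (baseline) after the delivery of the educational material". Question 6: "Follow-up surveys and confirmations will be conducted via phone calls". Behavioral Intervention/Task Details puts one 45-minute self-report survey inside the three-hour event.

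**The concern.** In a one-group pre-post study each woman is her own control. Three things are needed: a measurement before the education, a record that links it to the measurement after, and an analysis of the difference. The plan secures none of them clearly.

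- The test paragraph permits a paired analysis but does not require one, and the only specific test elsewhere is for two independent groups.
- Whether a key exists depends on which sentence is followed.
- Read literally, the sentence on the month 0 survey would remove the pre-measure altogether.

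At stake is the precision of the H1 result. Lost matching or a missing pre-measure cannot be repaired after data collection.

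**Working it through.** **The plan's own figure.** The sample-size text gives 10 women from 80% confidence, SD 0.5 and a 5% margin. The margin formula gives (1.2816 × 0.5 / 0.05)² = 164.2, so 165. A two-group t-test for a difference of 0.10 with SD 0.5 (two-sided 5%, 80% power) needs 393 per group. So 10 does not follow from its inputs, and 20 has no calculation behind it. This text cannot serve as the specification of the analysis.

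**Inputs for the pairing check.** n = 20 is from the plan. The rest are assumptions because the documents give none: two-sided 5%, pre-post correlation r = 0.3, 0.5, 0.7, true gain d = 0.5, 0.8, 1.0 SD.

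**Formulas.** Paired: dz = d / √(2(1 − r)); power from the noncentral t with n − 1 degrees of freedom and noncentrality dz√n. For d = 0.5 and r = 0.5: dz = 0.5, noncentrality 0.5 × √20 = 2.24, power 56%. Unpaired: simulated bivariate normal pairs analysed with the pooled two-sample t-test.

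| Gain | Paired power, r = 0.3 / 0.5 / 0.7 | Unpaired power, r = 0.3 / 0.5 / 0.7 |
|---|---|---|
| 0.5 SD | 43% / 56% / 78% | about 31% / 29% / 25% |
| 0.8 SD | 82% / 92% / 99% | about 72–73% / 76% / 80% |
| 1.0 SD | 95% / 99% / 100% | about 91% / 94% / 97% |

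With no true gain, the unpaired test rejects in about 2.1%, 0.7% and 0.1% of trials instead of 5%, so the error is conservative.

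**Precision.** The 95% half-width unpaired is t(38) × √(2/20) = 2.024 × 0.316 = 0.64 SD. Paired it is t(19) × √(2(1 − r)/20) = 0.55, 0.47 and 0.36 SD.

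**Is the post survey phoned?** Education (90 minutes) plus one survey (45) leaves 45 of the event's 180 minutes, which the plan gives to break and lunch. So one survey fits, not two.

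- If that survey is the post-test, it is in person. This fits question 4 of Study Procedures, which offers paper or a QR code after the education and schedules baseline surveys separately.
- If it is the pre-test, the post-test may be the phoned follow-up. Consent taken at the education session fits this reading.

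The documents do not decide. Only on the second reading, with the no-key sentence followed and the woman not supplying her own code, would a caller holding a name and number be unable to match the record.

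**Yes/no uptake.** If 20 women answered no before and 2 answer yes after, the exact (Clopper-Pearson) 95% interval is 1.2% to 31.7%; for 0 of 20 the upper limit is 16.8%. Fewer women at risk of changing widens this. An exact McNemar test of 2 changes against 0 gives p = 2 × 0.5² = 0.50; 6 against 0 are needed for p = 2 × 0.5⁶ = 0.031.

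**Which scores can be paired.** Nine scales appear on both the pre-test and post-test lists. Self-efficacy does not match: one unnamed scale before, a general and a screening-specific scale after.

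**The case against.** The strongest reply is that this is missing detail. A t-test or ANOVA for pre-post differences includes the paired t-test and repeated-measures ANOVA. Each woman has a unique ID, and most of the key text assumes a key. The study is a training pilot with no power claim to break, and the error is conservative. Much of this stands, and it limits the point.

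Four stronger readings are tempting and are not supported:

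- **That the plan prescribes an unpaired test.** It does not. The two-group t-test is a sample-size assumption, and question 6 disclaims any power analysis. The analysis text in Study Population, question 3, also breaks off in our copy where it turns to comparisons, so a test named there cannot be excluded.
- **That follow-up surveys will be unmatched.** This needs several conditions, none established.
- **That the result would be falsely positive.** With positive within-woman correlation the opposite holds.
- **That a control arm survives in the wording on both groups.** The same answer refers to two phases, focus group and trial, so the phrase may mean those.

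The reply does not dispose of the contradictions. The key sentences cannot both be followed, a survey given after the education is not a baseline, and the two-group t-test cannot be run.

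**Conclusion.** The point holds as a cheap improvement worth making before data collection. The plan does not secure the within-woman analysis that H1 needs: no paired test is named in the available text, the key statements conflict, use of one ID across both surveys is not stated, and the baseline timing contradicts the pre-test survey. The cost depends on the true gain. It is large at 0.5 SD (power lower by roughly 12, 28 or 53 percentage points as r rises) and small by 1.0 SD (about 3 to 5 points). These figures rest on assumed effects, correlations and a two-sided 5% level; the survey form is not in our copy. Non-matching remains a risk to close off, not a finding.

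**What to change.** 1. **Statistical Tests paragraph.** Analyse each score measured with the same instrument at both times by a paired t-test on within-woman differences, with a 95% confidence interval and the Wilcoxon signed-rank test as sensitivity analysis. Include self-efficacy only if a common scale is used before and after.
2. **Matching.** State that one study ID goes on the pre and post survey in every mode. Reconcile questions 3 and 9 of Data Confidentiality and Storage so that a restricted key exists until matching is complete and is then destroyed. If surveys are phoned, the principal investigator can put the ID on each form before the call, within the access rule already written.
3. **Timing.** State in Study Procedures, question 4, that the baseline survey is completed before the education and the post survey after it, and whether the post survey is in person or by phone.
4. **Two-group text.** Remove the intervention-versus-control t-test from the sample-size answer and the two-arm wording from the background; clarify which groups the month 0 sentence means.
5. **Uptake and primary outcome.** Question 6 names screening uptake as primary, while the aims name awareness; reconcile these. Report uptake as the number newly answering yes among women who answered no before, with an exact 95% interval.

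The cost is protocol wording. The one real downside is that a restricted name-to-ID key exists for a limited time.
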